# 7.7 Safety

### **7.7.1 Extent of Exposure**

Duration of exposure of each study drug, ie, plitidepsin, dexamethasone, and the regulatory-approved antiviral for those patients randomised to the control arm (ie, remdesivir or favipiravir), will be defined in days as:

(date of last dose of the relevant study drug taken – date of first dose of the relevant study drug taken) + 1.

If date of first dose date is missing then date of randomisation visit will be used.

Duration of exposure (as a continuous variable), total number of days with doses administered, the number of days where total amount was administered, the number of days where total amount was not administered and the number of infusions interrupted (as continuous and categorical variables only for plitidepsin, and the regulatory-approved antiviral for those patients randomised to the control arm, ie, remdesivir or favipiravir) will be listed and summarized using descriptive statistics for each treatment group and each study drug for the As Treated population.

### 7.7.2 Adverse Events

All AEs recorded on the eCRF will be coded using the MedDRA dictionary (Version 24 [or a later version if updated during the study]) and classified as TEAEs as follows:

• TEAEs are events with start date on or after the date of first dose of any study drug or events with start date prior to the date of first dose of any study drug whose severity worsens on or after the date of first dose of any study drug. If the event started on the date of first dose of the first study drug administration however it is ticked as the event started prior to first study drug administration on Day 1 in the eCRF, it will not be considered as a TEAE.

All AE data will be listed by treatment group with TEAE status flagged in the listing. In addition, listings of grade  $\geq$ 3 AEs, SAEs, AEs leading to discontinuation of any study drug, AEs resulting in death and AEs of special interest will be produced.

The AEs of special interest will be based on MedDRA version 24.0. The terms that determine the AEs of special interest are:

- For Rhabdomyolysis, Musculoskeletal disorders and CPK increases:
  - Rhabdomyolysis/Myopathy (SMQ)
  - Additional PTs: Back pain, Pain in extremity, Arthralgia
- For Hypersensitivity reactions:
  - Hypersensitivity (SMQ)
- For Cardiac events:
  - Cardiomyopathy (SMQ)
  - Cardiac arrhythmias (SMQ)
  - Cardiac failure (SMQ)
  - Additional PTs: Acute myocardial infarction, Cardiovascular insufficiency, Coronary artery disease, Myocardial infarction, Angina pectoris, Aortic valve incompetence, Aortic valve sclerosis, Atrial thrombosis, Cardiac disorder, Degenerative aortic valve disease, Left ventricular hypertrophy, Mitral valve incompetence, Myocardial ischaemia, Pericardial effusion, Pericarditis, Subendocardial ischaemia, Tricuspid valve incompetence, Blood creatine phosphokinase MB increased, Blood pressure increased, Cardiac murmur, Electrocardiogram QRS complex abnormal, Electrocardiogram ST segment abnormal, Electrocardiogram ST segment depression, Electrocardiogram ST-T change, Electrocardiogram ST-T segment abnormal, Electrocardiogram T wave abnormal, Electrocardiogram T wave amplitude decreased, Electrocardiogram T wave inversion, Oxygen saturation decreased, Pulse abnormal, Respiratory rate,

Troponin increased, Troponin I increased, Troponin T increased, Acute respiratory failure, Apnoea, Dyspnoea exertional, Hyperventilation, Hypoventilation, Hypoxia, Tachypnoea, Diastolic hypertension, Hypovolaemic shock, Systolic hypertension.

- For Hepatobiliary disorders and Transaminase elevations:
  - Hepatobiliary disorders (SOC)
  - Liver function analyses (HLT)

The final list of terms that determine the AEs of special interest will be described in the 'Analysis Set Specification' document to ensure the latest MedDRA version is used for the analyses.

Summary tables of TEAEs by treatment group and overall plitidepsin will be produced for the As Treated population.

Assessment of AE severity will be based on the NCI-CTCAE, version 5.0.

A treatment-related TEAE to plitidepsin, dexamethasone or to the antiviral control arm, ie, the regulatory-approved antiviral for those patients randomised to the control arm (remdesivir or favipiravir), is an TEAE considered by the investigator as related to the corresponding study drug or with unknown/missing relationship to trial medication.

An overview table will summarize the number and percentage of patients with at least one of the following TEAEs, where patients with more than one TEAE in a particular category are counted only once in that category:

- Any TEAE;
- Any TEAE by severity;
- Any TEAE grade  $\geq$ 3;
- Any TEAE leading to discontinuation of any study drug;
- Any TEAE leading to death;
- Any treatment-related TEAE to any study drug;
- Any treatment-related TEAE grade  $\geq$ 3 to any study drug;
- Any treatment-related TEAE to any study drug leading to discontinuation of any study drug;
- Any treatment-related TEAE to any study drug leading to death;
- Any treatment-related TEAE to plitidepsin;
- Any treatment-related TEAE grade  $\geq$ 3 to plitidepsin;
- Any treatment-related TEAE to plitidepsin leading to discontinuation of any study drug;
- Any treatment-related TEAE to plitidepsin leading to death;

- Any treatment-related TEAE to dexamethasone;
- Any treatment-related TEAE grade  $\geq$ 3 to dexamethasone;
- Any treatment-related TEAE to dexamethasone leading to discontinuation of any study drug;
- Any treatment-related TEAE to dexamethasone leading to death;
- Any treatment-related TEAE to antiviral control arm;
- Any treatment-related TEAE grade  $\geq$ 3 to antiviral control arm;
- Any treatment-related TEAE to antiviral control arm leading to discontinuation of any study drug;
- Any treatment-related TEAE to antiviral control arm leading to death;
- Any serious TEAE;
- Any serious TEAE grade  $\geq$ 3;
- Any serious TEAE leading to discontinuation of any study drug;
- Any serious TEAE leading to death;
- Any serious treatment-related TEAE to any study drug;
- Any serious treatment-related TEAE grade  $\geq$ 3 to any study drug;
- Any serious treatment-related TEAE to plitidepsin;
- Any serious treatment-related TEAE to dexamethasone;
- Any serious treatment-related TEAE to antiviral control arm;
- Any TEAE of special interest;
- Any TEAE grade  $\geq$ 3 of special interest;
- Any TEAE of special interest leading to discontinuation of any study drug;
- Any TEAE of special interest leading to death

The number and percentage of patients reporting each TEAE will be summarized by treatment group and overall plitidepsin, SOC and grouped PT for the As Treated population. Tables will be sorted alphabetically by SOC. Grouped PTs will be sorted by descending overall total. The following summaries will be produced:

- TEAEs, by SOC and grouped PT;
- TEAEs by grouped PT;
- TEAEs by maximum severity, SOC and grouped PT;
- TEAEs leading to discontinuation of any study drug by SOC and grouped PT;
- TEAEs leading to death by SOC and grouped PT;

- Treatment-related TEAEs to any study drug (plitidepsin, dexamethasone or antiviral control arm) by SOC and grouped PT;
- Treatment-related TEAEs to any study drug (plitidepsin, dexamethasone or antiviral control arm) by maximum severity, SOC and grouped PT;
- Treatment-related TEAEs to plitidepsin by SOC and grouped PT;
- Treatment-related TEAEs to plitidepsin by maximum severity, SOC and grouped PT;
- Treatment-related TEAEs to dexamethasone by SOC and grouped PT;
- Treatment-related TEAEs to dexamethasone by maximum severity, SOC and grouped PT;
- Treatment-related TEAEs to antiviral control arm by SOC and grouped PT;
- Treatment-related TEAEs to antiviral control arm by maximum severity, SOC and grouped PT;
- Serious TEAEs by SOC and grouped PT;
- Serious TEAEs by maximum severity, SOC and grouped PT;
- Serious treatment-related TEAE to any study drug (plitidepsin, dexamethasone or antiviral control arm) by SOC and grouped PT;
- Serious treatment-related TEAE to any study drug (plitidepsin, dexamethasone or antiviral control arm) by maximum severity, SOC and grouped PT;
- Serious treatment-related TEAE to plitidepsin by SOC and grouped PT;
- Serious treatment-related TEAE to dexamethasone by SOC and grouped PT;
- Serious treatment-related TEAE to antiviral control arm by SOC and grouped PT.
- TEAEs of special interest by SOC and grouped PT;
- TEAEs of special interest by maximum severity, SOC and grouped PT.

In the above summaries, patients with more than one AE within a particular SOC are counted only once for that SOC. Similarly, patients with more than one AE within a particular grouped PT are counted only once for that grouped PT. For summaries by maximum severity, patients with multiple AEs within a particular SOC or grouped PT will be counted under the category of their most severe AE within that SOC or grouped PT.

The final list of SOCs and PTs that are grouped after physician's review will be described in the 'Analysis Set Specification' document to ensure the latest MedDRA version is used for the analyses.

In addition, summary tables of deaths and their causes (adverse event or other) by treatment group and overall plitidepsin will be produced for the As Treated population.

No formal statistical comparisons of AEs between treatment groups will be performed.

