### Table 14.3.2.6.1 TEAEs of special interest by System Organ Class and Grouped Preferred Term (As Treated Population)

System Organ Class Grouped Preferred Term [a]	Plitidepsin 2.5mg (N=XXX) n (%) E	Plitidepsin 1.5mg (N=XXX) n (%) E	Plitidepsin Total (N=XXX) n (%) E	Control Arm (N=XXX) n (%) E
Number of Patients with at least one TEAE of special interest	xxx (xxx.x) xxx	xxx (xxx.x) xxx	xxx (xxx.x) xxx	xxx (xxx.x) xxx
System Organ Class 1 Grouped Preferred Term A Grouped Preferred Term B	xxx (xxx.x) xxx xxx (xxx.x) xxx xxx (xxx.x) xxx			
System Organ Class 2 Grouped Preferred Term C etc.	xxx (xxx.x) xxx xxx (xxx.x) xxx			

N = number of patients in analysis set; n = number of patients with data available; % = percentages are calculated based on N as the denominator; E = number of events.

TEAE = Treatment Emergent Adverse Event.

Note: TEAEs are events with start date on or after the date of first dose of any study drug or events with start date prior to the date of first dose of any study drug whose severity worsens on or after the date of first dose of any study drug. If the event started on the date of first dose of the first study drug administration however it is ticked as the event started prior to first study drug administration on Day 1 in the eCRF, it is not considered as a TEAE.

[a] Within a system organ class, patients may have reported more than one grouped preferred term. Patients are counted once for each grouped preferred term and each system organ class. MedDRA version & meddra.

Reference: Listing 16.2.7.4

- Table template TAE002.
- Sort alphabetically by system organ class and descending grouped preferred term in the total column. Where grouped preferred terms tie these should be sorted alphabetically.
- Assign the version of MedDRA Dictionary to & meddra. macro variable as XX.X and update the version of MedDRA Dictionary used for coding as needed.

System Organ Class Grouped Preferred Term [a] Maximum Severity [b]	Plitidepsin 2.5mgPlitidepsin 1.5mg(N=XXX)(N=XXX)n (%) En (%) E		Plitidepsin Total (N=XXX) n (%) E	Control Arm (N=XXX) n (%) E
Number of Patients with at least one TEAE of special interest	xxx (xxx.x) xxx	xxx (xxx.x) xxx	xxx (xxx.x) xxx	xxx (xxx.x) xxx
System Organ Class 1	xxx (xxx.x) xxx	xxx (xxx.x) xxx	xxx (xxx.x) xxx	xxx (xxx.x) xxx
Grouped Preferred Term A	xxx (xxx.x) xxx	xxx (xxx.x) xxx	xxx (xxx.x) xxx	xxx (xxx.x) xxx
Grade 1	xxx (xxx.x) xxx	xxx (xxx.x) xxx	xxx (xxx.x) xxx	xxx (xxx.x) xxx

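### Section 7.7.2 of the SAP defines four special-interest risk groups, but no planned table counts patients per group

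*SAP*

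**What the plan says.** Section 7.7.2 builds four groups, each with its own term list:

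- "For Rhabdomyolysis, Musculoskeletal disorders and CPK increases": one SMQ plus three added PTs.
- "For Hypersensitivity reactions": one SMQ.
- "For Cardiac events": three SMQs plus a long PT list, which includes "Acute respiratory failure, Apnoea, Dyspnoea exertional, Hyperventilation, Hypoventilation, Hypoxia, Tachypnoea".
- Hepatobiliary disorders and transaminase elevations: one SOC plus a separately listed HLT for liver function analyses.

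The final lists are left to the Analysis Set Specification.

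The planned outputs are as follows. The overview has a line for "Any TEAE of special interest" and three more, for grade 3 or higher, leading to discontinuation and leading to death; Table 14.3.1.2 matches. The detailed summaries are "TEAEs of special interest by SOC and grouped PT" and the same by maximum severity. In the shell of Table 14.3.2.6.1 the only total is "Number of Patients with at least one TEAE of special interest", followed by SOC and grouped PT rows. Its footnote counts a patient once per grouped PT and once per SOC. Listing 16.2.7.4 shows SOC, PT, verbatim term, dates, severity, relationship, action and outcome. The post-hoc addendum adds no special-interest output by group.

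**The concern.** The plan takes the trouble to define four distinct risks and then never reports on them as such. Section 3.4 names the frequency of special-interest TEAEs as a safety endpoint, and Section 2.1.3.2 sets out to compare each dose with control on adverse events. A reader of the report will want to know how many patients per arm had a muscle, hypersensitivity, cardiac or hepatic event, and whether that differs between 1.5 mg and 2.5 mg.

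The only special-interest counts that count each patient once across terms and SOCs are the pooled ones, and these are exposed to background. The cardiac list contains respiratory terms such as hypoxia and acute respiratory failure, and Section 2.2 describes a population admitted to hospital and needing oxygen for COVID-19. Events of the disease itself can fill the pooled lines in every arm.

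**Working it through.** **1. Outputs checked for a group row, line or column**

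| Output | How events are arranged | Patients per group? |
|---|---|---|
| Table 14.3.1.2 | four lines, each pooled over groups | no |
| Table 14.3.2.6.1 | one pooled row, then SOC and PT | no |
| Table 14.3.2.6.2 | the same, by maximum severity | no |
| Listing 16.2.7.4 | by patient, with SOC/PT/verbatim | no group column |
| Table 14.3.8.1 | laboratory grades and selected TEAEs, by subgroup | no |
| Post-hoc addendum | no special-interest output by group | no |

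**2. Can the group count be recovered from the SOC and PT rows?** If two rows of one group show a and b patients, the group count lies between max(a, b) and a + b. With a = 10 and b = 8 (invented), that is 10 to 18. The hepatic group shows the problem in the SAP's own terms. The HLT is listed beside the SOC, which has a purpose only if it brings in terms outside that SOC, so the SOC row is not the group total.

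**3. Dilution in the pooled lines (illustration).** The SAP gives no event rates, so all rates here are assumed, and the groups are taken as independent. With group rate p and combined rate b from the other three groups:

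pooled rate = 1 − (1 − p)(1 − b)

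As a scale of visibility only, take n = 203 per arm (Section 2.2, planned size), two-sided 0.05 and p̄ = (p₀ + p₁)/2:

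power = Φ{[|p₁ − p₀|√n − 1.96√(2p̄(1 − p̄))] / √[p₀(1 − p₀) + p₁(1 − p₁)]}

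For a group at 3% versus 10%:

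| Line | Control | Plitidepsin | Ratio | Power |
|---|---|---|---|---|
| Group alone | 3% | 10% | 3.33 | 82% |
| Pooled, b = 20% | 1 − 0.97×0.80 = 22.4% | 1 − 0.90×0.80 = 28.0% | 1.25 | 25% |
| Pooled, b = 40% | 1 − 0.97×0.60 = 41.8% | 1 − 0.90×0.60 = 46.0% | 1.10 | 13% |
| Pooled, b = 60% | 1 − 0.97×0.40 = 61.2% | 1 − 0.90×0.40 = 64.0% | 1.05 | 8% |

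Section 8 records that recruitment stopped early, so the real arms are smaller than 203; the SAP gives no final number. With an assumed 70 per arm, and control rates of 30% hepatic, 20% cardiac, 3% hypersensitivity and 5% muscle, let the muscle rate rise to 20%. The pooled rate moves from 1 − 0.70×0.80×0.97×0.95 = 48.4% to 1 − 0.70×0.80×0.97×0.80 = 56.5%. The chance that a 95% interval for the difference excludes zero is about 77% for the muscle row and about 16% for the pooled line. The pooled figure becomes 28% if the hepatic and cardiac rates are 15% and 10%, and 11% if they are 40% and 30%.

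**The case against.** The case on the other side has several sound parts.

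- **The trial could still produce the counts.** A reader might infer that group frequencies are lost. They are not: Listing 16.2.7.4 together with the final term list would allow them to be derived patient by patient. What stands is that no planned table prints them.
- **Nothing stated is missing.** A reader might see a contradiction with the safety endpoint. Section 3.4 names special-interest TEAEs as one category and promises no frequency per group, so the planned tables deliver what it says.
- **Dilution is not general.** It applies to the overview lines. In the SOC/PT tables a signal is split rather than diluted, and if one PT carried most of the excess, its row would show it almost in full. The power contrast above compares a group row only with the pooled line.
- **Power is not the SAP's yardstick.** Section 7.7.2 rules out formal comparisons of adverse events.
- **Other tables help.** The CTCAE shift tables cover CPK, ALT, AST, bilirubin and troponin T. Table 14.3.6.2 covers QTcF outliers, and Table 14.3.8.1 has CPK, ALT and AST rows by subgroup. These are laboratory and ECG counts, not patients with a TEAE in a group, and none covers hypersensitivity.
- **Not every group is shown to cross SOCs.** For the muscle group this depends on the content of the SMQ, which the SAP does not reproduce. The hepatic definition carries the point by itself.

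The Analysis Set Specification is said to fix term lists and groupings, not to add outputs, so it does not close the gap.

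**Conclusion.** The point holds as a worthwhile, inexpensive improvement to the safety reporting. The four groups are defined, yet no planned table gives patients per arm for any of them, and the SOC and PT rows cannot be added up to supply the figure. That conclusion comes from the document alone and needs no assumed rate.

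The size of the dilution does depend on assumptions: independent groups and invented rates. Within the range tried, a 3.33-fold excess shows as a ratio of 1.05 to 1.25 in a pooled line. It should be read as scale, not as evidence that a signal was missed. No estimate is biased and no definition is wrong.

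**What to change.** In Section 7.7.2 and the shells:

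- Make the four groups the first-level rows of Tables 14.3.2.6.1 and 14.3.2.6.2, counting each patient once per group, with SOC and grouped PT beneath.
- Add lines per group to Table 14.3.1.2: any, grade 3 or higher, serious, leading to discontinuation, leading to death. Keep the existing pooled lines.
- Add a group column to Listing 16.2.7.4. The addendum already does the equivalent for nosocomial infections, with an infection-type entry in Listing 16.2.7.5.

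The cost is one grouping variable in the adverse-event dataset and a few more rows; the term lists already exist. A term that belongs to two groups will appear in both, so the group rows need not add up to the pooled row, and a footnote should say so. The addendum puts database lock at 26 April 2023, so outputs added now should be labelled as added after lock, noting that the groups themselves stand in SAP version 4.0 of 21 April 2023.

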### 7.7.3 Laboratory Evaluations

Data for the haematology, serum chemistry, and coagulation analytes received from central laboratory will be listed and summarized by treatment group and overall plitidepsin, and visit. Haematology and serum chemistry analytes from local laboratories recorded at Screening in the eCRF will be listed only. If data for any additional analytes are also received then these will be listed only.

Immunology and Serological SARS CoV 2 data are summarised within the other secondary efficacy endpoints.

Haematology	Serum Chemistry	
Red Blood Cell Count	Alanine aminotransferase (ALT)	
Haemoglobin	Aspartate aminotransferase (AST)	
Haematocrit	Alkaline phosphatase	
White Blood Cell Count	Gamma-Glutamyltransferase (GGT)	
Neutrophils	LDH	
Eosinophils	Total Bilirubin	
Basophils	Direct Bilirubin	
Lymphocytes	Glucose (fasting)	
Monocytes	Sodium	
Platelet Count	Potassium	
Transunalagy	Calcium (adjusted)	
Immunology	Magnesium	
CRP	Blood Urea Nitrogen	
Ferritin	Creatinine	
IL-1β	Calculated Creatinine Clearance (Cockcroft-Gault equation)	
IL-6	Creatine Phosphokinase (CPK)	
IL-10	Albumin	
TNFa	Amylase	
	Lipase	
Other Samples	Procalcitonin	
Pregnancy tests (females	Troponin T	
only)	N-terminal pro-B-type natriuretic peptide (NT-pro-BNP)	
Coagulation	Serological SARS CoV 2 testing	
D-dimer	IgG	

All central Laboratory data will be reported in International System of Units. Local Laboratory data will be listed in the Units that they were collected in the eCRF. Outof-reference-range values will be flagged as high (H) or low (L) in the listings. For analysis purposes, values preceded by a "<" or a ">" sign (ie, those below or above the limits of quantification) will be considered equal to the lower or upper limit of quantification, respectively.

Central laboratory data will be summarized by visit using standard descriptive statistics by treatment group and overall plitidepsin for the As Treated population. Changes from Baseline will also be summarized. For post-Baseline, only data from scheduled visits will be included in the summary tables.

If more than 10% of the patients preform an unscheduled central laboratory assessment at the same relative day to the start date of study treatment then the central laboratory data will be also summarised at the specific relative day. In case of several unscheduled laboratory assessments at the same day we will use the worst result.

For each laboratory analyte, the Baseline value will be defined as last scheduled or unscheduled non-missing value from central Laboratory collected prior to the first dose of the first study drug administration. Central Laboratory assessments carried out on the day of first study drug administration are considered to have taken place before the study drug administration, if the corresponding times have not been recorded.

For haematology and serum chemistry analytes, laboratory abnormalities from central Laboratory analytes will be graded according to NCI-CTCAE version 5.0. Shift tables presenting the number and percentage of patients cross-tabulating NCI CTC grade at baseline to the worst grade after baseline through the study (including results from unscheduled visits) will be provided by treatment group for the As Treated population. For analytes that have NCI-CTCAE gradings for both low and high values, low and high will be summarized separately. In the shifts of low values, any high values will be classified as normal and the worst low grade will be summarized. And in the shifts of high values, any low values will be classified as normal and the worst high grade will be summarized.

Haematology analyte	Low NCI CTC grade	High NCI CTC grade
Red Blood Cell Count	-	-
Haemoglobin	Х	Х
Haematocrit	-	-
White Blood Cell Count	Х	Х
Neutrophils (absolute)	Х	-
Eosinophils (absolute)	-	Х
Basophils (absolute)	-	-
Lymphocytes (absolute)	Х	Х
Monocytes (absolute)	-	-
Platelet count	Х	-

#### Statistical Analysis Plan

Sponsor Name: Pharma Mar S.A. Sponsor Protocol ID: APL-D-003-20

Labcorp Drug Development Study ID: 000000213894

Serum chemistry analyte	Low NCI CTC grade	High NCI CTC grade
ALT	-	Х
AST	-	Х
Alkaline phosphatase	-	Х
GGT	-	Х
LDH	-	Х
Total bilirubin	-	Х
Direct bilirubin	-	-
Glucose	Х	-
Sodium	Х	Х
Potassium	Х	Х
Calcium (adjusted)	Х	Х
Magnesium	Х	Х
Blood urea nitrogen	-	-
Creatinine	-	Х
Calculated creatinine clearance	-	-
СРК	-	Х
Albumin	Х	-
Amylase	-	Х
Lipase	-	Х
Procalcitonin	-	-
Troponin T	-	Х
NT-pro-BNP	-	-

For lymphocytes, neutrophils/lymphocytes ratio (NLR), ALT, CPK, Troponin T, NT-ProBNP, and procalcitonin, the median values together with the interquartile ranges will be plotted over time by treatment group and visit. Moreover, a spaghetti plot will also be used to represent the patient profile over time by treatment group.

